2.7 Data Handling Conventions and Transformations

Diabetes duration will be calculated as (Consent date – DM diagnosis date) / 365.25. It will be rounded to the whole year.

Body mass index (BMI) will be calculated as weight (kg) / [height (m)]². It will be displayed to 1 decimal place in listings, but will not be rounded or truncated prior to summarization

Estimated glomerular filtration rate (eGFR) will be calculated using the MDRD-4 equation: GFR in mL/min per 1.73 m² = 175 x SerumCr^{-1.154} x age^{-0.203} x 1.212 (if patient is African American) x 0.742 (if female).

Patients with missing data in Creatinine Serum, age, race, or gender will not have eGFR calculated.

If urine microalbumin value is reported as being too high for the laboratory to calculate a UACR, 5000 mg value for UACR will be used.

3 SUBJECT DISPOSITION

3.1 Subject Enrollment

The number and percent of subjects randomized for each site will be summarized overall and by treatment group. The denominator for the percent calculation will be number of subjects screened.

3.2 Disposition of Subjects

A summary of subject disposition will be provided overall and by treatment group, as appropriate. This summary will present the number of subjects screened, randomized, included in the safety analysis set, and the number and percent of subjects meeting the following criteria:

- Had known vital status at the end of the study
- Died
- Completed the study drug treatment (defined as on study drug at week 12 visit)
- Did not complete the study drug treatment (with summary of reasons for not completing the study treatment)
- Completed the study (defined as with visit at week 12)
- Completed the study (defined as with visit at week 12) and completed the study drug (defined as on study drug at week 12 visit)
- Had at least one in-person visit
- Had visit at week 6 and week 12
-
-

The denominator for the percent of subjects in each category will be the number of subjects randomized.

No inferential statistics will be generated. A data listing of reasons for premature study treatment/study discontinuation will be provided.

3.3 Extent of Exposure

3.3.1 Study Drug Compliance

Study drug compliance will be derived using the Study Drug Accountability at 12 weeks. Proportion of study drug compliance is defined as proportion of patients respond 'Currently taking study drug' at 12 weeks.

Summaries will be provided by treatment group for the safety analysis set.

3.3.2 Duration of Exposure to Study Drug

Duration of exposure to study drug will be defined as (last dose date – first dose date of double-blind treatment phase + 1), regardless of temporary interruptions in study drug administration, and will be expressed in weeks (shown to one decimal place, e.g., 4.5 weeks).

Duration of exposure to study drug will be summarized using descriptive statistics (sample size, mean, standard deviation, median, first quartile (Q1), third quartile (Q3), minimum, and maximum).

Summaries will be provided by treatment group for the safety analysis set.

3.3.3 Adherence with Study Drug

- The actual number of tablets ingested will be calculated using the Study Drug Accountability CRF:

Total number of tablets dispensed - total number of tablets returned.

- The expected number of tablets ingested will be calculated based on the Study Drug Dispensed CRF and Study Drug Accountability CRF:

Total number of days supposed on study drug ([date of last dose of study drug - start date + 1])

- Adherence rate
$$100(\text{total number of tablets ingested}) / (\text{expected number of tablets ingested}).$$

Adherence will be capped at 100% for summarization. Patients with unreturned bottles will be excluded from adherence calculations.

Descriptive statistics for adherence (sample size, mean, standard deviation, median, Q1, Q3, minimum, and maximum) will be provided by treatment group and overall for the safety analysis set.

4 Endpoints variables

4.1 Primary endpoints:

- Kansas City Cardiomyopathy Questionnaire (KCCQ) clinical summary score at 12 weeks

4.2 Secondary endpoints:

- Kansas City Cardiomyopathy Questionnaire (KCCQ) overall summary score at 12 weeks
- NTproBNP at 6 and 12 weeks
- BNP at 6 and 12 weeks
- Six-minute walk test at 12 weeks
- HbA1c at 6 and 12 weeks
- Proportion of patients with a \geq 5pts increase in KCCQ clinical summary score at 12 weeks and proportion of patients with a \geq 5pts increase in KCCQ overall summary score at 12 weeks
- Proportion of patients with a \geq 20% decrease in 6 and 12 weeks NTproBNP
- Proportion of patients with a \geq 5pts increase in KCCQ at 12 weeks and a \geq 20% decrease in 6 and 12 weeks NTproBNP
- Weight at 6 and 12 weeks
- Systolic blood pressure at 6 and 12 weeks.

Average of the three measures of supine systolic blood pressure at each time point will be used.

4.3 Exploratory Outcome Variables

- Composite mean hierarchical-rank clinical score.

All patients will receive a global rank endpoint based on time to death (tier 1), time to HF hospitalization or urgent HF visit (tier 2), or change in KCCQ clinical summary score from baseline to 12 weeks. The variable for ranking the patients will be derived as follows.

- Patients dying during the study will have a value of $0 + (\text{study days from randomization to death})$. Patients with missing vital status at the end of trial will be excluded from the analysis. Patient dying during the study but with no mortality date will use the average of the last known alive date and the patient's scheduled 12 weeks follow-up date.

- Patients who did not die but had multiple occurrences of HF hospitalization or urgent HF visit will have a value of 200 – number of occurrences.
- Patients who did not die but have only one HF hospitalization or urgent HF visit will have a value of 200 + (study days from randomization to the occurrence of HF hospitalization or urgent HF visit). Patients known to have an event but event date is unknown will be imputed using the median rank based on the rank of other patients in this category.
- Patients who did not die and did not experience HF hospitalization or urgent HF visit will have a value of 400 + (change in KCCQ clinical summary score from baseline to week 12).

Patients with missing KCCQ at 12 weeks who didn't die and didn't have HF events will be excluded. A sensitivity analysis will be performed where these patients will be kept in the analysis and the KCCQ values will be imputed using multiple imputation as described in section 2.6.

- Number of heart failure hospitalizations and proportion of patients experienced heart failure hospitalizations
- Number of urgent heart failure visits and proportion of patients with urgent heart failure visits
- Total number of heart failure hospitalizations and urgent heart failure visits and proportion of participants who experienced any heart failure hospitalizations and urgent heart failure visits.

For the four endpoints above, only events positively adjudicated by the clinical event committee will be included. Events that occurred between screening and randomization, and between 12 weeks and 13 weeks will be excluded from this analysis. Events that occurred between the week 12 and week 13 study visits will be reported in a separate, supplemental analysis.

- Proportion of patients that progress to diabetes during the treatment period (within the subgroup of patients without diabetes at baseline only). Progression to diabetes is defined as a HbA1c of 6.5 or greater at either 6 week or 12 week follow-up.
- Average daily loop diuretic dose (furosemide equivalent)

The following equations will be used to convert doses to Furosemide equivalent:

- 40 mg Furosemide = 20 mg Torsemide = 2 mg Bumetanide = 50 mg Ethacrynic Acid
- When patient is not on a loop diuretic, dose = 0 mg.

- For subjects with dosing schedule reported as “as needed (prn)”, we will assume a twice a week dosing regimen for loop diuretic at the recorded dose.

In addition to comparing daily loop diuretic dose between treatment arms, we will also compare the proportion of patients who had their loop diuretic dose reduced or discontinued at any time during the treatment period.

- Change in NYHA Class at 6 and 12 weeks.

A 3-level categorical variable: 1) Decrease, 2) No change, 3) Increase. For patients missing NYHA class at 12 weeks, value at 6 weeks will be used.

- Echocardiography sub study endpoints: left atrial volume index and other measures of left ventricular diastolic function

Primary Endpoint

Left atrial volume index at 12 weeks

Exploratory endpoints:

- BSA
- LVEDD
- LVESD
- IVSd
- PWd
- Relative Wall Thickness
- LV Mass
- LV Mass Index
- Left ventricular end diastolic volume
- Left ventricular end systolic volume
- Estimated LVEF
- LVEF Calculated
- Left atrial dimension
- Left atrial volume
- Left atrial volume index
- E
- E/A
- E/E' medial
- E/E' lateral
- Tricuspid regurgitant velocity
- Longitudinal strain

5 Analyses of Baseline Characteristics

Patient demographics, baseline clinical characteristics, medical histories, and baseline labs will be described overall and by treatment group. Continuous measures will be summarized by mean \pm standard deviation and compared using Student's T-tests. Categorical variables will be summarized by frequency and percent and compared using χ^2 or Fisher's exact tests, as appropriate.

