5.9.8 Study Closure Visit

All randomized patients should return for their study closure visit (visit 8) as soon as possible, but no later than 1 week after the previously scheduled visit 7.

If a patient is unable to attend the study closure visit in person, telephone contact should be made to ascertain endpoint and AE information. At the study closure visit, physicians caring for the patient will decide which medication the patient should receive as part of his/her ongoing clinical care.

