5.10 Withdrawal from study

Patients are at any time free to withdraw from the study (i.e., discontinue study medication permanently and withdraw from visit assessments), without prejudice to further treatment (withdrawal of consent). Withdrawal of consent from the study must be ascertained and documented by the investigator. Such patients will always be asked about the reason(s) and the presence of any AEs. The reason for permanent discontinuation of treatment with the study medication and the date of the last intake of the study medication must be documented.

5.10.1 Patients permanently discontinuing from study medication should be given conventional therapy, if applicable, and should always be asked to continue to attend protocol visits

If the patient denies any additional protocol follow-up and officially withdraws consent from the study one of the alternatives a) to c) should be followed:

- At the time of discontinuation of treatment and withdrawal of consent from continued assessment the patient should, if possible, undergo the PTDV. The patient should return all study medication
- If the patient does not agree to this option (which must be documented), a modified PTDV (eg, a telephone contact) should be arranged. The approach taken should be documented. The patient should return all study medication
- If the patient does not agree to a) or b) this must be documented in the patient's medical record. The patient should return all study medication.

To ensure validity of study data, it is very important to collect as much data as possible throughout the study and especially vital status (dead or alive) at the SCV. The investigator or delegate will therefore attempt to collect information on all patients' vital status from publicly available sources at the SCV, in accordance with local regulations, even if informed consent has been withdrawn completely.

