10.7 Study timetable and end of study

The study is expected to start in December 2016 and to end in October 2018. Planned treatment duration in the study is 13 weeks. will notify investigators when

recruitment is complete. The end of the entire study is defined as 'the last visit of the last patient undergoing the study'.

The study may be terminated at individual centers if the study procedures are not being performed according to GCP, or if recruitment is slow.

may also terminate the entire study prematurely if concerns for safety arise within this study or in any other study with dapagliflozin.

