6.3 Exploratory outcome variables

6.3.1 Composite mean hierarchical-rank clinical score.

The composite hierarchical-rank clinical score will be analyzed on the safety dataset. Patients with missing KCCQ values at 12 weeks will be excluded unless they died or had HF hospitalizations or urgent HF visits. Win ratio will be used to compare the rank score of each patient in the dapagliflozin arm with each patient in the placebo group. Each comparison will result in a “win”, “loss” or “tie” for the patient in the dapagliflozin group if the analysis value of the patient in the dapagliflozin group is higher, lower or equal to the analysis value of the patient in the placebo group, respectively. Within the dapagliflozin group, total number of wins will be divided by the total number of losses (ties are split evenly between wins and losses) to form the Win Ratio statistic of the dapagliflozin group against the placebo group (Pocock et al 2012). The confidence interval of the win ratio statistic will be calculated as described in Gasparyan et al 2020 (see APPENDIX).

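### The hierarchical composite drops every patient with missing end-of-trial vital status, including patients whose HF event before week 12 already fixes most of their rank (minor)

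*SAP*

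**What the plan says.** SAP 4.3 introduces the composite with "All patients will receive a global rank endpoint". Scores are built in tiers:

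- death: 0 plus the day of death;
- several HF events: 200 minus their number;
- one HF event: 200 plus its day;
- neither: 400 plus the week-12 change in KCCQ clinical summary score.

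Within the death tier it adds: "Patients with missing vital status at the end of trial will be excluded from the analysis". No exception follows.

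For the composite and the three HF-event endpoints, SAP 4.3 also states: "Events that occurred between screening and randomization, and between 12 weeks and 13 weeks will be excluded from this analysis". The event window therefore closes at week 12.

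Two further rules deal with missing KCCQ, not missing vital status. SAP 6.3.1 says "Patients with missing KCCQ values at 12 weeks will be excluded unless they died or had HF hospitalizations or urgent HF visits". For patients with no death, no HF event and no week-12 KCCQ, SAP 4.3 adds: "A sensitivity analysis will be performed where these patients will be kept in the analysis", using multiple imputation.

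The SAP does not define the end of the trial. The protocol gives three pointers:

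- Section 5.10.1 stresses collecting data, "especially vital status (dead or alive) at the SCV" (the study closure visit).
- Section 5.9.8 puts that visit "no later than 1 week after the previously scheduled visit 7", that is, at week 13.
- Section 10.7 uses a trial-level milestone ("The end of the entire study is defined as" the final visit of the last patient).

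**The concern.** The exclusion depends on a fact that the rank often does not need. A patient with an adjudicated HF event by week 12 who is then lost has an uncertain tier (2, or 1 if death followed), but the ordering against every event-free patient is settled. Deleting that patient removes a known poor outcome. If event patients are lost mainly from one arm, the win ratio shifts.

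The second possible loss depends on how the undefined term is read. A patient who attended week 12 was alive throughout the window, and a death after week 12 would not count anyway. If vital status is judged at week 13 or later, such a patient could be removed with every input to the score in hand.

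The only sensitivity analysis for excluded patients covers missing KCCQ in patients with neither death nor HF event. It brings back neither group.

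**Working it through.** **1. Does an HF event fix the rank against event-free patients?** KCCQ scores run from 0 to 100 (Protocol 6.6), so the change is at least −100 and an event-free score is at least 400 − 100 = 300. By day 84 (week 12), a single HF event scores at most 200 + 84 = 284, several events at most 200 − 2 = 198, and a death at most 84. All are below 300. An HF-event patient of unknown later vital status therefore loses to every event-free patient in either case. Only comparisons with other event or death patients are uncertain.

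**2. What happens to each type of patient?**

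| Patient | SAP 4.3 vital-status rule | SAP 6.3.1 KCCQ rule |
|---|---|---|
| HF event, KCCQ present, vital status missing | excluded | not addressed |
| HF event, KCCQ and vital status both missing | excluded | kept |
| No event, KCCQ present, vital status missing (possible only if judged after week 12) | excluded | not addressed |
| No event, KCCQ missing, known alive | not addressed | excluded; imputed in the sensitivity analysis |

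The two sections give different instructions only in the second row.

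**3. How many patients?** The documents give no expected rate of missing vital status. Of about 320 randomised, 1% is 3 patients, 2% is 6 and 5% is 16.

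**4. How far does the win ratio move?** The documents state no power or event rate for the composite, so there is no plan figure to reproduce. The KCCQ difference of 4.7 and SD of 13.7 come from SAP 1.3. The sample is 160 × 0.9 = 144 per arm after the plan's 10% loss. HF-event rates of 5% (dapagliflozin) and 10% (placebo) are assumptions, giving 7.2 and 14.4 expected event patients.

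Let a and b be the event proportions among patients kept in the dapagliflozin and placebo arms, and let q be the chance that an event-free dapagliflozin patient beats an event-free placebo patient:

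- q = Φ(4.7 / (13.7 × √2)) = Φ(0.2426) = 0.5958
- P(win) = (1 − a)b + (1 − a)(1 − b)q + ½ab
- win ratio = P(win) / (1 − P(win))

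With nobody dropped: 0.95 × 0.10 + 0.95 × 0.90 × 0.5958 + ½ × 0.05 × 0.10 = 0.0950 + 0.5094 + 0.0025 = 0.6069. The win ratio is 0.6069 / 0.3931 = 1.544.

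| Event patients dropped (dapagliflozin, placebo) | a | b | P(win) | Win ratio |
|---|---|---|---|---|
| 0, 0 | 7.2/144 = 0.0500 | 14.4/144 = 0.1000 | 0.6069 | 1.544 |
| 1, 2 | 6.2/143 = 0.0434 | 12.4/142 = 0.0873 | 0.6057 | 1.536 |
| 2, 4 | 5.2/142 = 0.0366 | 10.4/140 = 0.0743 | 0.6043 | 1.527 |
| 0, 2 | 0.0500 | 0.0873 | 0.6018 | 1.511 |
| 0, 4 | 0.0500 | 0.0743 | 0.5964 | 1.478 |

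**5. Range over other assumptions.** This was simulated with 160 per arm, HF-event rates of 3% vs 6% or 5% vs 10%, and vital status missing in 10–30% of event patients and 1–5% of others. About 5 to 22 of 320 patients are excluded, of whom about 1 to 7 have an HF event. The mean win ratio moves from 1.522 to 1.519 at the mild end and from 1.545 to 1.528 at the severe end. With equal event rates (5%) and 2% missing throughout, it does not move materially (1.424 and 1.425).

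For scale, the sampling 95% range of a single trial's win ratio under the step 4 assumptions is roughly 1.2 to 2.0.

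**The case against.** Several stronger readings are tempting, and the documents do not support them.

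*That SAP 6.3.1 contradicts SAP 4.3 outright.* It does not. SAP 6.3.1 concerns missing KCCQ and does not lift the vital-status exclusion. The conflict is confined to HF-event patients missing both items.

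*That week-12 completers are certainly lost.* This depends on the undefined term. In favour of a week-12 reading, SAP 4.3 uses the scheduled 12-week date as the upper limit when a death date is missing, and SAP 3.2 defines study completion by the week-12 visit. On that reading this group is empty. Against it, SAP 3.2 lists known vital status at the end of the study as a separate item, and the protocol collects vital status at the closure visit. Protocol 10.7 defines a trial-level milestone and need not govern a patient-level rule. The HF-event part stands on either reading.

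*That patients leave because they are ill, so the win ratio is biased toward 1.* Neither document says why patients would be lost. The larger shifts in the table require losing placebo event patients only, which is 14% (2 of 14.4) to 28% (4 of 14.4) of that arm's assumed events.

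*That many patients are at risk.* Missing vital status should be rare. The protocol allows telephone contact when the closure visit is missed (5.9.8) and searches public sources for patients who refuse follow-up (5.9.6) or withdraw consent (5.10.1).

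The endpoint is also one of eight exploratory objectives, with no multiplicity control. These objections stand and they limit the point. They do not supply the missing exception for a known HF event.

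**Conclusion.** The concern holds in a limited form. As written, SAP 4.3 discards patients with an adjudicated HF event before week 12 when later vital status is unknown, although their order against every event-free patient is fixed. Whether it also discards week-12 completers depends on a term the SAP leaves undefined. The protocol's collection of vital status at week 13 makes that reading plausible but not certain.

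Under the assumed 5% versus 10% event rates, the effect is about 0.01 to 0.02 on a win ratio of 1.54 if losses are proportional. It is about 0.03 to 0.07 if only placebo event patients are lost. The event and missingness rates are assumptions, not document figures. The primary conclusion is unaffected. Severity: minor.

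**What to change.** Replace the exclusion sentence in SAP 4.3 with wording such as:

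*Vital status is assessed at the 12-week cut-off; a patient with a week-12 visit or later contact is alive at that cut-off. A patient with an adjudicated HF event by week 12 and unknown later vital status is ranked on that event. Patients with unknown vital status at week 12, no HF event and no week-12 KCCQ are excluded.*

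Keep the existing exclusion, and its multiple-imputation sensitivity analysis, for patients known to be alive and event-free with no week-12 KCCQ. They have no score, so the new wording must not be read as returning them to the main analysis.

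Add a sensitivity analysis for patients of unknown vital status, stating that imputing their KCCQ assumes they are alive. Repeat the same rules in SAP 6.3.1 so that both sections yield one dataset.

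The cost is SAP wording and one extra analysis run, with no new visits or data. It should be settled before unblinding.

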4 STUDY POPULATION

Voluntary participation will be sought from patients with chronic heart failure with preserved systolic function at outpatient general cardiology and specialized heart failure clinics. Informed consent will be obtained from potentially eligible participants prior to initiating screening visit procedures.

It is expected that approximately 60% (174 patients) of the study cohort will have pre-diabetes or normal glucose metabolism (no diabetes), and therefore, the proportion of patients with established Type 2 diabetes may be capped at 45% (~146 patients). The proportion of patients with permanent atrial fibrillation may be capped at 33% of the study cohort (105 patients).

Randomization will be stratified by diabetes status (diabetes vs. no diabetes), permanent atrial fibrillation status (Yes vs. No), and by patients' participation in the echocardiography sub-study.

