2 GENERAL CONSIDERATIONS FOR DATA ANALYSES

2.1 Analysis Data Sets

Efficacy and safety analyses will be performed on data from the following analysis sets:

- Enrolled patients set (EPS) will consist of all patients who signed the informed consent. This data set will be used to summarize the patient disposition data.
- Modified intention to treat set (modified ITTS) is defined as all patients who have been randomized to study treatment, have received at least one dose of study medication, and have sufficient evaluable data for endpoint ascertainment during follow up. For clarity, patients with no evaluable data for a particular outcome during follow up will be excluded from the analyses of these respective endpoints. Subjects will be analysed according to the randomization group. The modified ITTS data set will be used for the primary, secondary, and selected exploratory (, NYHA class, loop diuretic dose, progress to DM, left atrial volume index and other measures of left ventricular diastolic function) efficacy endpoints. Progress to DM will be assessed among participants in the modified ITTS who had no diabetes at baseline. Left atrial volume index and other measures of left ventricular diastolic function will be assessed among participants who are in the modified ITTS dataset and also in the Echocardiography sub study.
- On-treatment set (OTS) includes all subjects in the modified ITTS. Primary and secondary endpoint measurements will be excluded for the follow-up time point(s) when subjects were temporarily or permanently off the study drug at the time the corresponding measurements were obtained. The OTS data set will be used for a sensitivity analyses for the primary, secondary, and selected exploratory (composite hierarchical rank clinical score, NYHA class, loop diuretic dose) efficacy endpoints.
- The per protocol set (PPS) includes all subjects in the modified ITTS who did not have any major protocol deviations. Major protocol deviations, which are detailed in section 2.2, will be determined prior to unblinding of treatment groups. Subjects will be summarized according to actual treatment received regardless of the allocated treatment. This will be used for a sensitivity analysis for the primary efficacy endpoints only.

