2.6 Missing Data

There are three possible sources for missing data:

1. Deaths
2. Administrative error
3. Premature study terminations

Missing data due to deaths is expected to be very low (fewer than 10 patients) because of the short follow-up period. Missing data due to administrative error is believed to be negligible due to the study management procedures and is also believed to be missing completely at random (MCAR). For patients who drop out of the study prematurely, a premature treatment discontinuation visit (PTDV) will be scheduled for them, whenever possible, to get the last assessment. The PTDV assessment will be carried forward to the next follow-up time point. For partially completed KCCQ questionnaires, the scoring algorithm accommodates a limited number of skipped responses. Values that are missing at randomization but available at screening will be imputed using the value at screening. Primary, secondary, and exploratory endpoints will be analyzed among patients for whom all relevant data for the given endpoint can be calculated.

For KCCQ scores, additional sensitivity analysis will be conducted using multiple imputation to account for missing values. IVEware (Raghunathan et al. 2002) will be used to perform the multiple imputation which employs iterative sequential regression to sample missing values from the predictive distribution of each variable, conditional on all other variables included in the imputation model. The following variables will be included in the imputation model: baseline KCCQ scores, sex, baseline eGFR, history of diabetes (DM), history of permanent AFib, baseline LVEF, baseline NYHA class, heart failure hospitalization during the trial duration, urgent heart failure visit during the trial duration, and covariates used as subgroup variables in section 2.3. Additionally, the imputation model will also include all follow up

assessments available for KCCQ scores, eGFR, NTproBNP, BNP, Hgb, loop Diuretic dose, 6-minute walk test.

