6.3.4 Heart failure hospitalizations and urgent heart failure visits

Will be analyzed in a manner analogous to that described in 6.3.2.

6.3.5 Proportion of patients that progress to diabetes during the treatment period (within the subgroup of patients without diabetes at baseline only)

Will be analyzed in a manner analogous to that described in 6.3.2.

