3.3	Admission for an acute coronary syndrome (ST-elevation MI, non-ST-elevation MI, or unstable angina), percutaneous coronary intervention, or cardiac surgery during the study period.	Other	To be decided on a case by case basis
4. Patient received prohibited concomitant medication but study treatment not discontinued:			
4.4.1	SGLT2 inhibitors	Other	Only the efficacy endpoints before the start of prohibited medication will be included in PPS analysis
5. Patient received incorrect investigational treatment/dose			
5.0	Patient took incorrect treatment or damaged Investigational Drug Kit	MIA	To be decided on a case by case basis
5.1	Major compliance issues <80% or >120% compliance with IP dosing in double blind treatment period	MIA	To be decided on a case by case basis
5.2	Patient randomized but never took IP	MIA	To be decided on a case by case basis

5.3	Overdose	MIA	To be decided on the case by case basis
6. Protocol-required procedure not adhered to:			
6.0	Study data collection has not been stopped when subject decided to withdraw their consent from the study completely	Other	No exclusion from PPS Data collected after consent withdrawal to be excluded from data base
6.1	Patients with absence of NT-proBNP data at randomization visit and having values at Screening visit.	Other	No exclusion from PPS Values from screening visit will be used to impute the values at randomization visit.
6.2	Patients with absence of baseline NT-proBNP data at both screening and randomization visits	Other	Excluded from the NT-proBNP analyses
6.3	Patients with no NT-proBNP values after randomization	Other	Excluded from the NT-proBNP analyses
6.4	Patients with absence of baseline KCCQ clinical summary score at randomization visit	Other	Excluded from the ITTS KCCQ analyses
6.5	Patients with no KCCQ clinical summary score after randomization	Other	Excluded from ITTS KCCQ analyses
6.6	Patients with absence of baseline 6-minute walk assessment at randomization visit	Other	Excluded from the 6-minute walk analyses
6.7	Patients with no 6-minute walk assessment after randomization	Other	Excluded from 6-minute walk analyses
6.8	Patients with missing values in the covariates: gender, Hx AFib, AFib type, Hx DM, eGFR at randomization, lvef at randomization	Other	No exclusion from PPS Excluded from the first and second primary analysis

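### Progression to diabetes carries no baseline HbA1c condition, so diabetes already present at entry can be counted as progression

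*SAP*

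**What the plan says.** **Event.** SAP 4.3: "Progression to diabetes is defined as a HbA1c of 6.5 or greater at either 6 week or 12 week follow-up". One value at one visit is enough.

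**At-risk group.** SAP 4.3 limits the endpoint to patients "within the subgroup of patients without diabetes at baseline only" (a restriction without a laboratory criterion). SAP 2.1 repeats it and names the analysis set: "Progress to DM will be assessed among participants in the modified ITTS who had no diabetes at baseline".

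**How diabetes status is labelled.** The imputation model in SAP 2.6 lists "history of diabetes (DM" as a variable. The covariate list in SAP 10.2 (item 6.8) reads "gender, Hx AFib, AFib type, Hx DM, eGFR at randomization", which puts diabetes as a history item beside a laboratory value dated to randomisation. Protocol section 4 describes the two strata differently. On one side, "the proportion of patients with established Type 2 diabetes may be capped at 45" percent. On the other, about 60% of the cohort "will have pre-diabetes or normal glucose metabolism (no diabetes".

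**Analysis.** The whole instruction in SAP 6.3.5 is "Will be analyzed in a manner analogous to that described in 6.3.2". Section 6.3.2, written for heart failure hospitalisation, specifies the safety dataset, a chi-square or Fisher comparison, and in addition a Cox model adjusted for sex, eGFR, diabetes, permanent atrial fibrillation and LVEF.

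**Data available.** Under Protocol Table 1 (footnotes b and c), HbA1c is measured at screening, randomisation, week 6 and week 12.

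**The concern.** Entry status and outcome appear to be judged by different rules. The outcome is an HbA1c threshold, whereas the labels suggest that entry status comes from the medical history. A patient with unrecognised diabetes therefore enters as not diabetic and becomes an event at the first follow-up value of 6.5 or more, although nothing has progressed.

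Two things are at stake. The reported progression rate would include prevalent disease. The treatment comparison would also be hard to read, because Protocol 1.3.4 expects dapagliflozin to improve glucose control in patients with diabetes or prediabetes. A patient who enters above 6.5 and is brought below it by treatment would look like a case of diabetes prevented.

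Separately, the cross-reference to 6.3.2 brings in features that do not suit this endpoint.

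**Working it through.** **1. Is there a baseline HbA1c condition anywhere?** The places where one could stand are:

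| Place | What it gives | HbA1c condition at entry |
|---|---|---|
| SAP 4.3 | event rule; patients without diabetes at baseline | none |
| SAP 2.1 | modified ITT set, no diabetes at baseline | none |
| SAP 2.6 and 10.2 | diabetes named as a history variable | none |
| SAP 2.7 | diabetes duration from a diagnosis date | none |
| Protocol 4 | strata described in words | no cut-off |
| Protocol 4.1 and 4.2 | eligibility criteria | none |

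No place requires a value below 6.5 at screening or randomisation.

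**2. Size.** The plan states no rate, power or sample size for this endpoint, so there is no figure to reproduce. The illustration below uses one input from the protocol and two assumptions:

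- N = 174 evaluable patients without diabetes (Protocol 12.2; 0.60 × 290 = 174).
- u, assumed: share of these with entry HbA1c of 6.5 or more.
- i, assumed: true 12-week incidence in the rest.

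Prevalent cases = N × u. Incident cases = N × (1 − u) × i. Share of counted events that are prevalent = prevalent / (prevalent + incident), if all prevalent cases stay at or above 6.5.

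| u | i | Prevalent | Incident | Prevalent share |
|---|---|---|---|---|
| 2% | 5% | 174 × 0.02 = 3.5 | 174 × 0.98 × 0.05 = 8.5 | 29% |
| 5% | 3% | 174 × 0.05 = 8.7 | 174 × 0.95 × 0.03 = 5.0 | 64% |
| 10% | 1% | 174 × 0.10 = 17.4 | 174 × 0.90 × 0.01 = 1.6 | 92% |

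The first and last rows are the extremes over u = 2% to 10% and i = 1% to 5%. The range is wide because both inputs are assumed. It shows only that a small prevalent share can rival the true events.

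**3. Direction of the treatment comparison.** Assume no true incidence, entry values of 6.5 plus an exponential amount with mean 0.3, measurement SD 0.1 at each of two visits, and an event if either reading is 6.5 or more. By simulation, 97% of prevalent cases are counted on placebo. If the drug lowers HbA1c by 0.1, 0.2 or 0.3, then 84%, 64% or 46% are counted on active treatment. Prevention would appear where none occurred. If instead prevalent cases stay above 6.5 in both arms, they add equal expected counts to each arm and pull the comparison towards no difference. Either can happen.

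**4. What the reference to 6.3.2 brings in.**

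- The safety dataset, while SAP 2.1 assigns this endpoint to the modified ITT set.
- A Cox model, although HbA1c is seen only at two scheduled follow-up visits.
- A diabetes covariate that is constant within this subgroup.
- No adjustment for baseline HbA1c.

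**The case against.** **Status may be set by HbA1c in practice.** Protocol section 4 describes the group without diabetes in metabolic terms that a patient at 6.5 or more would not fit. Protocol 3.2 says the screening laboratory panel, including HbA1c, serves eligibility, yet 4.1 and 4.2 contain no HbA1c criterion, so classifying diabetes status is a plausible use of it. This stands to the extent that classification by history is an inference from labels and is not stated. If sites did classify on screening HbA1c, most of the problem disappears. But neither document says so, and two analysts could build different denominators from the same text. The randomisation sample goes to a central laboratory (Protocol 7.2) and is drawn at the visit where treatment is assigned, so it could hardly have informed the stratum.

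**The analysis problems largely resolve themselves.** SAP 2.1 is explicit on the analysis set, the chi-square or Fisher test in 6.3.2 already suits a proportion, and a constant covariate drops out of a model. That is fair, and it makes the cross-reference a drafting fault only.

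**HbA1c is covered elsewhere.** It is a secondary endpoint evaluated separately in patients without type 2 diabetes and adjusted for baseline. This lowers the stakes but does not give the progression endpoint a sound definition.

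**Stronger readings that the documents do not support.** A reader might infer that prevalent cases simply dilute any effect; the working shows that the opposite can occur. A reader might also size the problem by measurement noise near the cut-off. With an assumed within-person CV of 2%, rounding to one decimal and independent errors, P = 1 − Φ((6.45 − m)/(0.02m)) and the chance on either of two visits is 1 − (1 − P)². That gives 57% for a stable true value of 6.4 and 22% for 6.3. But the CV is assumed, the documents do not say how many patients lie there, and these patients do not have diabetes at entry. A baseline restriction would not remove that noise, so it is no measure of this point.

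**Conclusion.** The concern holds as a gap in the at-risk definition. As written, the rule allows diabetes present at entry to be counted as progression, and where that happens it overstates the rate. The direction of bias in the treatment comparison is not established.

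The conclusion rests on two things: the absence of any entry HbA1c condition, which is plain in the text, and classification by history, which is inferred. The 29% to 92% range is illustrative and depends on assumed prevalence and incidence.

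The severity is minor. This is one of eight exploratory endpoints, SAP 2.5 makes no multiplicity adjustment for them, and the primary analysis is untouched.

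**What to change.** In SAP 4.3 and 2.1, define the at-risk group as modified ITT patients with no history of diabetes and HbA1c below 6.5 at both screening and randomisation. State there whether a single follow-up value suffices.

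In SAP 6.3.5, replace the reference to 6.3.2 with a self-contained instruction: compare proportions in the modified ITT set by chi-square or Fisher's exact test, with no Cox model and no diabetes covariate. Any model adjusted for baseline HbA1c should be supportive only and use a method suited to sparse events. The illustrative true event count above is in single figures, too few for a logistic model with several covariates.

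The cost is a few lines of SAP text before unblinding and a slightly smaller denominator. No new data are needed. Noise near the threshold will remain and should be acknowledged when the result is reported.
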